Bone Mineral Loss  Pediatric < 21 Years	BMD t-score or z-score -2.5 to -1.0  BMD z-score -2.5 to -1.0	BMD t-score or z-score < -2.5  BMD z-score < -2.5	Pathological fracture (including loss of vertebral height)  Pathological fracture (including loss of vertebral height)	Pathologic fracture causing life-threatening consequences  Pathologic fracture causing life-threatening consequences
Myalgia (non-injection site)	Muscle pain causing no or minimal interference with usual social & functional activities	Muscle pain causing greater than minimal interference with usual social & functional activities	Muscle pain causing inability to perform usual social & functional activities	Disabling muscle pain causing inability to perform basic self-care functions
Osteonecrosis	NA	Asymptomatic with radiographic findings AND No operative intervention indicated	Symptomatic bone pain with radiographic findings OR Operative intervention indicated	Disabling bone pain with radiographic findings causing inability to perform basic self-care functions

SYSTEMIC				
	Grade 1	Grade 2	Grade 3	Grade 4
Acute Systemic Allergic Reaction	Localized urticaria (wheals) with no medical intervention indicated	Localized urticaria with medical intervention indicated OR Mild angioedema with no medical intervention indicated	Generalized urticaria OR Angioedema with medical intervention indicated OR Symptomatic mild bronchospasm	Acute anaphylaxis OR Life-threatening bronchospasm OR laryngeal edema
Chills	Symptoms causing no or minimal interference with usual social & functional activities	Symptoms causing greater than minimal interference with usual social & functional activities	Symptoms causing inability to perform usual social & functional activities	NA
Fatigue Malaise	Symptoms causing no or minimal interference with usual social & functional activities	Symptoms causing greater than minimal interference with usual social & functional activities	Symptoms causing inability to perform usual social & functional activities	Incapacitating fatigue/malaise symptoms causing inability to perform basic self-care functions
Fever (nonaxillary)	37.7°C to 38.6°C 99.8°F to 101.5°F	38.7°C to 39.3°C 101.6°F to 102.8°F	39.4°C to 40.5°C 102.9°F to 104.9°F	> 40.5°C > 104.9°F
Pain- Indicate Body Site See also Injection Site Pain, Headache, Arthralgia, and Myalgia	Pain causing no or minimal interference with usual social & functional activities	Pain causing greater than minimal interference with usual social & functional activities	Pain causing inability to perform usual social & functional activities	Disabling pain causing inability to perform basic self-care functions OR Hospitalization (other than ER visit) indicated
Unintentional Weight Loss	NA	5% to 9% loss in body weight from baseline	10% to 19% loss in body weight from baseline	≥ 20% loss in body weight from baseline OR Aggressive intervention indicated [eg, tube feeding or total parenteral nutrition]

INJECTION SITE REACTION				
	Grade 1	Grade 2	Grade 3	Grade 4
Injection Site Pain (pain without touching) Or Tenderness (pain when area is touched)	Pain/tenderness causing no or minimal limitation of use of limb	Pain/tenderness limiting use of limb OR Pain/tenderness causing greater than minimal interference with usual social & functional activities	Pain/tenderness causing inability to perform usual social & functional activities	Pain/tenderness causing inability to perform basic self-care function OR Hospitalization (other than ER visit) indicated for management of pain/tenderness
Injection Site Reaction (Localized), > 15 Years	Erythema OR Induration of 5 × 5 cm to 9 × 9 cm (or 25–81 × cm  )	Erythema OR Induration OR Edema > 9 cm any diameter (or > 81 cm  )	Ulceration OR Secondary infection OR Phlebitis OR Sterile abscess OR Drainage	Necrosis (involving dermis and deeper tissue)
Pediatric ≤ 15 Years	Erythema OR Induration OR Edema present but ≤ 2.5 cm diameter	Erythema OR Induration OR Edema > 2.5 cm diameter but < 50% surface area of the extremity segment (eg, upper arm/thigh)	Erythema OR Induration OR Edema involving ≥ 50% surface area of the extremity segment (eg, upper arm/thigh) OR Ulceration OR Secondary infection OR Phlebitis OR Sterile abscess OR Drainage	Necrosis (involving dermis and deeper tissue)
Pruritis Associated with Injection See also Skin: Pruritis (itching—no skin lesions)	Itching localized to injection site AND Relieved spontaneously or with < 48 h treatment	Itching beyond the injection site but not generalized OR Itching localized to injection site requiring ≥ 48 h treatment	Generalized itching causing inability to perform usual social & functional activities	NA

ENDOCRINE/METABOLIC				
	Grade 1	Grade 2	Grade 3	Grade 4
Lipodystrophy (eg, back of neck, breasts, abdomen)	Detectable by study participant or caregiver (for young children and disabled adults)	Detectable on physical exam by health care provider	Disfiguring OR Obvious changes on casual visual inspection	NA
Diabetes Mellitus	NA	New onset without need to initiate medication OR Modification of current meds to regain glucose control	New onset with initiation of indicated med OR Diabetes uncontrolled despite treatment modification	Life-threatening consequences (eg, ketoacidosis, hyperosmolar non-ketotic coma)
Gynecomastia	Detectable by study participant or caregiver (for young children and disabled adults)	Detectable on physical exam by health care provider	Disfiguring OR Obvious on casual visual inspection	NA
Hyperthyroidism	Asymptomatic	Symptomatic causing greater than minimal interference with usual social & functional activities OR Thyroid suppression therapy indicated	Symptoms causing inability to perform usual social & functional activities OR Uncontrolled despite treatment modification	Life-threatening consequences (eg, thyroid storm)
Hypothyroidism	Asymptomatic	Symptomatic causing greater than minimal interference with usual social & functional activities OR Thyroid replacement therapy indicated	Symptoms causing inability to perform usual social & functional activities OR Uncontrolled despite treatment modification	Life-threatening consequences (eg, myxedema coma)
Lipoatrophy (eg, fat loss from the face, extremities, buttocks)	Detectable by study participant or caregiver (for young children and disabled adults)	Detectable on physical exam by health care provider	Disfiguring OR Obvious on casual visual inspection	NA

GENITOURINARY				
	Grade 1	Grade 2	Grade 3	Grade 4
Intermenstrual Bleeding (IMB)	Spotting observed by participant OR Minimal blood observed during clinical or colposcopic exam	Intermenstrual bleeding not greater in duration or amount than usual menstrual cycle	Intermenstrual bleeding greater in duration or amount than usual menstrual cycle	Hemorrhage with life-threatening hypotension OR Operative intervention indicated
Urinary Tract obstruction (eg, stone)	NA	Signs or symptoms of urinary tract obstruction without hydronephrosis or renal dysfunction	Signs or symptoms of urinary tract obstruction with hydronephrosis or renal dysfunction	Obstruction causing life-threatening consequences

INFECTION				
	Grade 1	Grade 2	Grade 3	Grade 4
Infection (any other than HIV infection)	Localized, no systemic antiꞑbial treatment indicated AND Symptoms causing no or minimal interference with usual social & functional activities	Systemic antiꞑbial treatment indicated OR Symptoms causing greater than minimal interference with usual social & functional activities	Systemic antiꞑbial treatment indicated AND Symptoms causing inability to perform usual social & functional activities OR Operative intervention (other than simple incision and drainage) indicated	Life-threatening consequences (eg, septic shock)

**Basic Self-care Functions:** Activities such as bathing, dressing, toileting, transfer/movement, continence, and feeding.

**Usual Social & Functional Activities:** Adaptive tasks and desirable activities, such as going to work, shopping, cooking, use of transportation, pursuing a hobby, etc.

## LIST OF ABBREVIATIONS

AASLD	American Association for the Study of Liver Diseases
AE	adverse event
ALT	alanine aminotransferase
ARV	antiretroviral
AST	aspartate transaminase
BMI	body mass index
CI	confidence interval
CSR	clinical study report
eCRF	electronic case report form
eGFR	estimated glomerular filtration rate
EMEA	European Medicines Agency
FAS	full analysis set
HCV	hepatitis C virus
HIV	human immunodeficiency virus
HLT	high level term
HLGT	high level group term
IFN	interferon
LLT	lower level term
LLOQ	lower limit of quantitation
MedDRA	Medical Dictionary for Regulatory Activities
NDA	New Drug Application
PEG	pegylated interferon
PK	pharmacokinetics
PT	preferred term
Q1	first quartile
Q3	third quartile
RBV	ribavirin
RNA	ribonucleic acid
SAE	serious adverse event
SAP	statistical analysis plan
SOC	system organ class
SOF	Sofosbuvir (GS-7977)
SVR	sustained virologic response
SVRx	sustained virologic response x weeks after stopping study drug
TE	treatment- emergent
TFLs	tables, figures, and listings
WBC	white blood cell

## **1. INTRODUCTION**

This statistical analysis plan (SAP) describes the statistical analysis methods and data presentations to be used in European Medicines Agency (EMA) 120-day response and American Association for the Study of Liver Diseases (AASLD) analysis for Study GS-US-334-0123 to support the New Drug Application (NDA) of sofosbuvir (GS-7977; SOF) for use in combination with other agents for the treatment of chronic hepatitis C (CHC) in adults.

### **1.1. Study Objectives**

#### **1.1.1. Primary Study Objectives**

- To determine the efficacy of treatment with Sofosbuvir (GS-7977; SOF) + ribavirin (RBV) by proportion of subjects with sustained viral response 12 weeks after discontinuation of therapy (SVR12)
- To evaluate the safety and tolerability of SOF + RBV as assessed by review of the accumulated safety data

#### **1.1.2. Secondary Study Objectives**

- To determine the proportion of subjects who attain SVR at 4 and 24 weeks after discontinuation of therapy (SVR4 and SVR24)
- To evaluate the kinetics of circulating HCV RNA during treatment and after treatment discontinuation
- To evaluate the emergence of viral resistance to SOF during treatment and after treatment discontinuation

#### **1.1.3. Exploratory Study Objectives**

- To identify or validate genetic markers that may predict the natural history of disease, response to therapy and/or the tolerability of medical therapies through genetic discovery research (eg, pharmacogenomics), in subjects who provide their separate and specific consent
- To assess the effect of treatment on health related quality of life

## **1.2. Study Design**

### **1.2.1. Design Configuration, Subject Population and Treatment Groups**

This is an open-label study in subjects with chronic genotype 1, 2, and 3 HCV infection who are coinfecting with HIV-1. A total of 230 subjects with HCV infection (115 genotype 2 or 3 and 115 genotype 1) will be enrolled and treated with oral SOF 400 mg once daily plus weight based RBV (1000 or 1200 mg/day) in a divided daily dose for 12 or 24 weeks, depending on genotype and prior treatment experience as following:

- Group 1: Treatment-naive subjects with genotype 2 or 3 HCV infection received 12 weeks of treatment followed by 24 weeks of follow-up
- Group 2: Treatment-experienced subjects with genotype 2 or 3 infection received 24 weeks of treatment followed by 24 weeks of follow-up
- Group 3: Treatment-naive subjects with genotype 1 HCV infection received 24 weeks of treatment followed by 24 weeks of follow-up

Subjects will be categorized based on interferon (IFN) eligibility or prior treatment with PEG+RBV into 1 of the following categories:

- Treatment naive and IFN-eligible
- Treatment naive and IFN-ineligible
- IFN intolerant
- Nonresponse
- Relapse/Breakthrough

Equal enrollment of subjects with genotype 2 or 3 HCV infection and treatment-naive and treatment-experienced subjects will be targeted. Approximately 20% of the subjects enrolled will have evidence of compensated cirrhosis at Screening. Approximately 10% of the subjects enrolled will not be on antiretroviral (ARV) treatment.

Subjects will be maintained on similar timing of administration and dosing conditions for their ARV regimens during the study period as those prior to the study. Posttreatment follow-up visits will be performed for all subjects at 4 weeks following the last dose of study drug. Subjects with HCV RNA < lower limit of quantification (LLOQ) at posttreatment Week 4 will return at posttreatment Week 12 and 24 unless confirmed HCV relapse occurs. Safety assessments, including monitoring of HIV RNA and CD4 T-cell counts, will be performed at all study visits.

Depending on subject outcome of HCV RNA, subjects may subsequently be enrolled into 1 of 2 registry studies: Sequence Registry Study and SVR Registry Study.

### **Sequence Registry Study**

Subjects who do not achieve SVR, as well as those who achieve SVR and later become detectable, will be eligible for enrollment in the Sequence Registry Study. The purpose of the Sequence Registry Study will be to monitor the persistence of resistant mutations for up to 3 years after the last dose of study drug. The Sequence Registry Study is described in a separate protocol (GS-US-248-0123).

### **SVR Registry Study**

Subjects who achieve SVR at 24-weeks posttreatment will be eligible for enrollment in the SVR Registry Study. The purpose of the SVR Registry Study will be to evaluate durability of SVR for up to 3 years posttreatment. The SVR Registry Study is described in a separate protocol (GS-US-248-0122).

#### **1.2.2. Study Duration**

The total time to complete all study visits is up to approximately 40 weeks for subjects treated with 12 weeks of therapy and 52 weeks for subjects treated for 24 weeks of therapy including the following periods:

- 28-day (4-week) screening period
- 12 or 24 week treatment period
- Up to 24-week post-treatment period

#### **1.3. Sample Size and Power**

With approximately 55 treatment-naive subjects with genotype 2 or 3 HCV infection enrolled into the study, a 2-sided 95.0% confidence interval of the SVR12 rate will extend at most 12.8% in both directions from the observed SVR12 rate, assuming the expected SVR12 rate is 62%. With approximately 55 treatment-experienced subjects with genotype 2 or 3 HCV infection and 115 treatment-naive subjects with genotype 1 HCV infection enrolled into the study, the SVR12 rate will extend at most 12.9% and 8.7% respectively, assuming the expected SVR12 rate is 40% and 65% respectively.

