**Criteria for Evaluation:**

**Safety:** AEs, safety labs (including HIV-1 RNA and CD4 T-cell count and percent), 12-lead ECG, and vital signs will be collected throughout the study and through the Week 4 post-treatment visit. If greater than 20% of subjects enrolled on any specific ARV regimen experience virologic breakthrough, an evaluation of the safety of continuing enrollment of subjects on this specific ARV therapy will occur.

**Efficacy:** Efficacy will be evaluated using scheduled assessments of HCV RNA performed using COBAS TaqMan® HCV Test, v2.0 for Use with the High Pure System.

**PK:** A single PK blood sample will be collected at all subject visits while on treatment. The PK of GS-7977 and metabolite(s) (as appropriate) and/or ribavirin will be assessed.

---

---

**Statistical Methods:** The primary efficacy endpoint is SVR12 in all enrolled and treated subjects. Secondary efficacy endpoints include SVR4 and SVR24. Subgroup analyses will be performed for SVR12.

All continuous endpoints will be summarized using an 8-number summary (n, mean, standard deviation, median, Q1, Q3, minimum, maximum). All categorical endpoints will be summarized by number and percentage of subjects who meet the endpoint definition.

Safety endpoints will be analyzed by the number and percent of subjects with events or abnormalities for categorical values or 8-number summary (n, mean, standard deviation, median, Q1, Q3, minimum, maximum) for continuous data by treatment group.

With approximately 55 GT2/3 treatment-naïve subjects enrolled into the study, a two-sided 95.0% confidence interval of the SVR12 rate will extend at most 12.8% in both directions from the observed SVR12 rate, assuming the expected SVR12 rate is 62%. With approximately 55 GT2/3 treatment-experienced and 115 GT1 treatment-naïve subjects enrolled into the study, the SVR12 rate will extend at most 12.9% and 8.7% respectively, assuming the expected SVR12 rate is 40% and 65% respectively.

---

This study will be conducted in accordance with the guidelines of Good Clinical Practices (GCPs) including archiving of essential documents.

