## **9.8. Sample Size**

With approximately 55 GT2/3 treatment-naïve subjects enrolled into the study, a two-sided 95.0% confidence interval of the SVR12 rate will extend at most 12.8% in both directions from the observed SVR12 rate, assuming the expected SVR12 rate is 62%. With approximately 55 GT2/3 treatment-experienced and 115 GT1 treatment-naïve subjects enrolled into the study, the SVR12 rate will extend at most 12.9% and 8.7% respectively, assuming the expected SVR12 rate is 40% and 65% respectively.

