### 6.2. Analysis of the Efficacy Endpoint

The efficacy endpoints will be derived for all subjects in safety analysis set using observed HCV RNA data and imputation rule specified in section 3.6.

For analyses of HCV RNA < LLOQ (ie, < 25 IU/mL) by visit while on treatment, subjects will be assigned a value at each visit based on the categorical imputation rules described in Section **Error! Reference source not found.** The 2-sided 95% exact confidence interval (CI) based on Clopper-Pearson method will be provided for the proportion {20839}. The overall category for “HCV RNA < LLOQ” will be split into the following 2 subcategories: “< LLOQ TND” for subjects with target not detected and “< LLOQ detected” for subjects with < LLOQ in tabular displays.

The point estimate of SVR4 and SVR12 rate and 2-sided 95% exact confidence interval (CI) will be provided for each treatment group and for each treatment group within each subgroup specified in section 3.4. A Forest plot will graphically present estimates and 95% confidence intervals of SVR4 and SVR12 rates for each treatment group within each subgroup.

For the SVR12 endpoint analysis, a summary table of the number and percentage of subjects with SVR12, virologic failure, and other will be created. All subjects who achieve SVR12 will be categorized as SVR12. Virologic failure will be descriptively summarized as “on-treatment virologic failure” and relapse (which will be summarized by study drug completed yes or no). Subjects who do not achieve SVR12 and do not meet criteria for virologic failure will be categorized as other. The denominator for relapse will be the number of subjects who had HCV RNA < LLOQ on their last observed on-treatment HCV RNA measurement; otherwise, the denominator will be the number of subjects in the FAS.

Details regarding SAS programming are provided in the programming specifications in **Error! Reference source not found.** of this SAP.

A data listing of HCV genotype, cirrhosis, IL28B, scheduled visit, analysis visit window, date of HCV RNA sample collection, HCV RNA load (categorical and numeric), and change from baseline for on-treatment visits will be provided for the following:

- 1), subjects with HCV virologic failure in the FAS;
- 2), all subjects in the FAS
- 3), all subjects in the safety analysis set but not in FAS

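### The stated SVR12 precision (at most 12.8, 12.9 and 8.7 points) is a normal-approximation half-width at one assumed rate; the planned exact interval reaches 14.1, 14.1 and 9.4 points on its longer side

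*Combined protocol and SAP*

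**What the plan says.** The synopsis (Statistical Methods), protocol 9.8 and SAP 1.3 carry the same precision statement.

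- **Genotype 2/3 treatment-naive** (about 55 subjects, assumed SVR12 rate 62%): "a 2-sided 95.0% confidence interval of the SVR12 rate will extend at most 12.8% in both directions from the observed SVR12 rate".
- **Genotype 2/3 treatment-experienced** (about 55, assumed 40%) **and genotype 1 treatment-naive** (115, assumed 65%): "the SVR12 rate will extend at most 12.9% and 8.7% respectively, assuming the expected SVR12 rate is 40% and 65% respectively".

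None of the three places names an interval method.

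SAP 6.2 sets the analysis: "The point estimate of SVR4 and SVR12 rate and 2-sided 95% exact confidence interval (CI) will be provided for each treatment group". Its preceding paragraph, on HCV RNA by visit during treatment, names the method: "2-sided 95% exact confidence interval (CI) based on Clopper-Pearson method". SAP 8 lists the Clopper-Pearson paper and no other reference on intervals. SAP Appendix 2 gives PROC FREQ code with the binomial option for the exact interval, run on a data set called SVR12.

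**The concern.** The study has one regimen per group, no comparator, and no hypothesis test or success threshold for SVR12. The precision statement is therefore the whole content of the SAP section on sample size and power, and the only reason given for the numbers enrolled. It promises a symmetric upper bound on the distance from the observed rate to each limit. A Clopper-Pearson interval is asymmetric unless the observed rate is 50%, and its total width at these rates is larger than the Wald width. If the stated figures come from the Wald formula, the interval that will be reported does not keep the promise.

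**Working it through.** **Inputs.** From SAP 1.3: n = 55, 55 and 115; assumed rates 62%, 40% and 65%; two-sided 95% confidence. From SAP 6.2: an exact interval for SVR12, taken as Clopper-Pearson.

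**Step 1: reproduce the stated figures.** Wald half-width = 1.96 × √(p(1−p)/n).

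- 1.96 × √(0.62 × 0.38/55) = 12.83 points; stated 12.8.
- 1.96 × √(0.40 × 0.60/55) = 12.947 points; stated 12.9.
- 1.96 × √(0.65 × 0.35/115) = 8.72 points; stated 8.7.

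All three match after ordinary rounding. The alternatives do not: Wald with continuity correction gives 13.7, 13.9 and 9.2, and Wilson gives -13.2/+11.6, -11.9/+13.2 and -9.1/+8.1.

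**Step 2: the planned interval at the same rates.** For x responders out of n, the lower limit is the 2.5% quantile of Beta(x, n−x+1) and the upper limit is the 97.5% quantile of Beta(x+1, n−x). The count nearest to each assumed rate is used.

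| Count | Rate | 95% limits | Distances | Stated | Excess, longer side |
|---|---|---|---|---|---|
| 34/55 | 61.8% | 47.7 to 74.6 | -14.1/+12.8 | 12.8 | 1.3 |
| 22/55 | 40.0% | 27.0 to 54.1 | -13.0/+14.1 | 12.9 | 1.2 |
| 75/115 | 65.2% | 55.8 to 73.9 | -9.4/+8.6 | 8.7 | 0.7 |

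The shorter side is about equal to the stated figure in every group. Half the total width is 13.4, 13.5 and 9.0 points.

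**Step 3: how often the bound fails.** Sum the binomial probabilities, at the assumed rate, of all counts whose longer side exceeds the stated figure. The result is 0.9987, 0.9995 and 0.9986. The bound holds only at observed rates far from those assumed: at least 45/55 (82%) or at most 10/55 (18%), and at least 90/115 (78%) or at most 25/115 (22%).

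**Step 4: worst case over all counts.** The largest distance to either limit is 14.09 points for n = 55 and 9.56 for n = 115. Against the stated figures this is 14.09 − 12.8 = 1.3, 14.09 − 12.9 = 1.2 and 9.56 − 8.7 = 0.9 points.

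**Step 5: the bound under Wald itself.** The Wald half-width is largest near an observed rate of 50%: 1.96 × √(0.25/55) = 13.2 and 1.96 × √(0.25/115) = 9.1. A value computed at one assumed rate is therefore not a maximum, but the shortfall is only 0.3 to 0.4 points.

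**Step 6: can the group sizes explain it?** Splitting the 115 genotype 2/3 subjects as 57 and 58 leaves the longer side at 13.7 to 13.8 points. Keeping the longer side within the stated figures at the assumed rates would take about 66, 66 and 135 subjects.

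**The case against.** The best defence is that nothing was miscalculated. The formula was applied correctly, the text names no method, each figure is tied to an assumed rate, and a normal approximation is common in planning. SAP 6.2 will report the exact interval whatever the sample-size section says, and no decision rests on the difference. All of that stands, and it limits the point to a wrong statement of precision. It does not rescue the statement, because the text promises an upper bound in both directions around the observed rate and the planned interval breaks it at the plan's own assumptions.

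A second objection is that the SVR12 sentence says only that the interval is exact, and that Clopper-Pearson is named one paragraph earlier for another endpoint. That is so. The attribution is an inference, supported by the single interval reference and by the Appendix 2 code.

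A reader might also infer more than the documents support:

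- **That the group sizes contradict the enrolment target** (55 + 55 + 115 = 225 against 230). The sizes are given as approximate, and 55 is slightly conservative against half of 115.
- **That precision is wrongly missing for genotypes 2 and 3 separately.** These are display columns within each group in SAP 3.2, and the plan commits to precision only at group level.
- **That the Wald bound fails in most trials.** At the one-decimal precision stated, it fails in about 43% to 48% of trials at the assumed rates, and by at most 0.3 to 0.4 points.

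**Conclusion.** The precision statement is wrong as written in all three places. The figures are Wald half-widths at single assumed rates. The planned exact interval extends 14.1, 14.1 and 9.4 points on its longer side at those rates, about 0.7 to 1.3 points past the stated bound, with probability above 0.998 in each group. Over all possible counts the excess is at most 0.9 to 1.3 points. This rests on Clopper-Pearson being the exact method, on 55, 55 and 115 subjects being analysed, and, for the probabilities, on the assumed rates being true.

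One might conclude that the trial is too small or has lost power. The documents do not support that: there is no test to power and no precision threshold to meet. Nor is the exact interval wider on both sides, since its shorter side is about equal to the stated figure.

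A separate condition affects group 2 in this SAP. SAP 2.1 triggers the analysis on groups 1 and 3, and SAP 3.1.1 admits treatment-experienced subjects to the full analysis set only if they have completed the posttreatment Week 12 visit or left the study early. The denominator may then be below 55. The documents do not give it, so these sizes are assumptions: the worst case is 14.1 points for 55, 16.7 for 40 and 20.2 for 28.

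**What to change.** In the synopsis, protocol 9.8 and SAP 1.3:

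1. Name the two-sided 95% Clopper-Pearson interval as the basis of the precision figures, and name it for SVR12 in SAP 6.2 as well.
2. Give the lower and upper distances at the assumed rates: -14.1/+12.8 (62%, n = 55), -13.0/+14.1 (40%, n = 55) and -9.4/+8.6 (65%, n = 115).
3. Replace the symmetric bound with a worst case conditional on the number analysed: 14.1 points from the observed rate if 55 subjects are analysed, 9.6 if 115. The condition matters because enrolment is approximate; at 54 the worst case is already 14.2.
4. In the SAP only, add that group 2 precision at this data cut depends on how many of its subjects meet the full analysis set definition in SAP 3.1.1, with an illustration such as 16.7 points for an assumed 40.

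This costs only text. Enrolment and analysis do not change. The stated worst-case precision becomes about 0.9 to 1.3 points less favourable at the planned group sizes.
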